## **Study Protocol**

A total of 60 lower impacted wisdom teeth were extracted from 30 patients participating in the study. The study was conducted as a randomized controlled trial (closed envelope method). One mucosal or bone retention fully impacted wisdom tooth was extracted from each patient at a time. The tooth extraction on the other side of the same patient was performed 3 weeks later after postoperative complications were eliminated and the extraction site wound healed and the mouth opening returned to its previous value. Patients whose extraction sites did not heal were not included in the study. The wound closure technique to be applied to the tooth to be extracted was randomly decided by the closed envelope method. The side to which suture was applied after tooth extraction was determined as the control group, and the side to which cyanoacrylate tissue adhesive (Periacryl 90) was applied was determined as the experimental group.

All operations were performed by the same dentist. In Group 1, a full thickness gingival flap was lifted to reach the first tooth to be extracted and after the procedure, the gingiva was sutured with silk in the starting position, while in Group 2, the lifted full thickness flap of the second tooth to be extracted was brought to the starting position and tissue adhesive (Periacryl 90) was applied.

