## **Surgical Technique and Application**

The patients in the study were operated on by the same physician in the local operating room environment at the XXX University, Faculty of Dentistry, Department of Oral, Dental and Maxillofacial Surgery, in accordance with the rules of asepsis and antisepsis. It was planned to extract one mandibular wisdom tooth with mucosal or bone retention from each patient at a time. The tooth extraction on the other side was performed after the postoperative complications were eliminated and the extraction site wound healed and the mouth opening was restored. The wound closure technique to be used in the tooth extraction was determined by the closed envelope method and the surgical procedure was completed using a different technique in the other tooth extraction.

The oral cavity was cleaned with an antiseptic solution before surgery and the surgical field was prepared in accordance with aseptic conditions. Demographic data, preoperative mouth opening, facial landmark measurements, data regarding the impacted tooth and the operation were recorded in the anamnesis form. Inferior alveolar block anesthesia was performed with direct technique using 3 cc articaine hydrochloride 80 mg- Epinephrine 0.010 mg/ampule (Maxicaine VEM, Turkey) with 27 gauge dental syringes. The same equipment and local anesthetic were used for buccal anesthesia. Winter type envelope flap was preferred using a scalpel tip of No. 15 in the surgeries. Following the incision, the full thickness flap was lifted to reach the extraction area. In teeth with bone retention, the bone was lifted with a 1.6 mm diameter steel rond bur, fissure bur, surgical micromotor operating at 40,000 rpm and serum irrigation, and then the teeth were exposed. Then, the teeth were extracted with the help of a bein elevator. Irrigation was performed with physiological serum to prevent the heat generated during the bone removal procedure from damaging the living tissues. Teeth that could not be extracted in one piece due to their position were divided and extracted with a surgical micromotor. After extraction, the dental follicle was removed from the alveolar region with the help of curettes and clamps. The extraction socket and the bottom of the

mucoperiosteal flap were irrigated with plenty of physiological serum to remove bone particles and tissue residues.

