The tension-free wound lips were closed by selecting the wound closure technique with the closed envelope method and providing appropriate procedures. The wound closure technique determined as suture wound closure was determined as the relevant dental control group. After the extraction socket was cleaned and bleeding control was provided, the wound lips were prepared without tension. The surgical site was closed primarily with 3/0, 16 mm 3/8 round needle atraumatic silk sutures. Postoperative recommendations were informed to the patient verbally and in writing. For infection control, 1000 mg amoxicillin+clavunate containing medication was prescribed 2x1 for 5 days. For pain control, 600 mg ibuprofen group analgesic was prescribed and recommended to be used 2x1. Cold compress was recommended for the first 8 hours after the operation for edema control. Appointments were made for the patient to come for the 3rd day and 1-week check-ups after the procedure. When the patient came for the check-up 1 week later, his sutures were removed.

The extraction of the tooth to which cyanoacrylate tissue adhesive would be applied was also performed with the same protocol and the surgical site was closed with cyanoacrylate tissue adhesive (Periacryl 90). While applying the tissue adhesive, the wound site was isolated from blood and saliva with an aspirator and sponge. Periacryl 90 liquid tissue adhesive was dropped onto a sterile perforated tray. Tissue adhesive was drawn into the applicator with a sterile applicator. The wound lips were brought together and the tissue adhesive was applied in a single layer with the applicator. Care was taken to ensure a tension-free closure. After the application, 30 seconds were waited for polymerization. The wound site was checked and the operation was terminated. Appointments were made for the 3rd day and 1-week check-ups after the procedure. It was recommended that the wound site not be traumatized with a toothbrush for 48 hours.

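### The closure technique is said to be drawn by envelope, yet one sentence puts suture on the first extraction and adhesive on the second, and nothing reconciles the two

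*Combined protocol and SAP*

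**What the plan says.** Each of 30 patients has two lower wisdom teeth removed in separate operations about 3 weeks apart, one closed with silk suture and the other with cyanoacrylate adhesive.

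Three statements make closure the thing that was drawn:

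- Study Protocol: "The wound closure technique to be applied to the tooth to be extracted was randomly decided by the closed envelope method".
- Surgical Technique and Application: "The wound closure technique to be used in the tooth extraction was determined by the closed envelope method", followed by "the surgical procedure was completed using a different technique in the other tooth extraction".
- Later in the same section, at the closing step: "The tension-free wound lips were closed by selecting the wound closure technique with the closed envelope method".

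The groups are named by closure alone in both sections. Study Protocol has "The side to which suture was applied after tooth extraction was determined as the control group", with the adhesive side as the experimental group. Surgical Technique and Application has "The wound closure technique determined as suture wound closure was determined as the relevant dental control group".

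The last sentence of Study Protocol attaches an order. It begins "In Group 1, a full thickness gingival flap was lifted to reach the first tooth to be extracted", says that this flap was closed with silk, and continues for Group 2: "the lifted full thickness flap of the second tooth to be extracted was brought to the starting position and tissue adhesive".

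**The concern.** In a two-tooth, within-patient design, a random draw of which closure comes first keeps closure apart from operation order. Three statements can be read as describing such a draw. The Group 1 / Group 2 sentence, taken as it stands, describes a fixed order: suture at the first operation, adhesive at the second.

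The two operations are separate occasions, so a patient's second may differ from the first for reasons unrelated to closure, such as the patient's experience of the procedure. The documents give no estimate of such a difference, and the Statistical Analyses section mentions no handling of order. If the order was fixed, any difference of this kind would appear as an effect of closure. The reader cannot tell from the text which rule was followed.

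**Working it through.** **1. Inputs.** Study Protocol gives 30 patients and 60 teeth; 30 × 2 = 60, so that figure reproduces. It also gives the 3-week interval. The documents give no order counts and no order effect.

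**2. What the ordinals mean.** The sentence speaks of the first and second tooth in terms of extraction, and the extractions are weeks apart. The plain sense is therefore chronological. *First* and *second* could be loose labels for the two study teeth, but the text does not say so.

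**3. What the envelope assigned.** Two readings are possible.

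- *Reading A: the envelope set the closure at the first operation, and the other tooth received the other closure.* Surgical Technique and Application fits this better, because it places the envelope at wound closure and then gives the other tooth the different technique. It implies, but does not say outright, that the draw was made at the first operation.
- *Reading B: the envelope set which side received which closure, and the suture side was always operated on first.* This satisfies both the randomisation sentence and the Group 1 / Group 2 sentence of Study Protocol.

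**4. Reading A against the fixed order.** Assume a fair, independent draw for each patient. Let k be the number of suture-first patients, so that k ~ Binomial(30, 0.5).

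- P(k = 30) = 0.5^30 = 1 / 1,073,741,824 ≈ 9.3 × 10^-10.
- P(10 ≤ k ≤ 20) = 0.957.

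A suture-first order in every patient is therefore not a credible outcome of such a draw.

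**5. How much of an order effect enters the closure contrast.** Let τ be the true adhesive-minus-suture difference and δ the mean second-minus-first difference due to order. A suture-first patient has an expected within-patient contrast of τ + δ; an adhesive-first patient has τ − δ. Averaged over 30 patients:

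expected contrast = τ + δ × [k − (30 − k)] / 30 = τ + δ × (2k/30 − 1)

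- k = 30: 2 × 30/30 − 1 = 1, so all of δ enters.
- k = 20: 2 × 20/30 − 1 = 0.33, so one third enters.
- k = 15: 2 × 15/30 − 1 = 0, so none enters.

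Under a fair draw of order the mean of k is 15, so the expected bias is zero. At k = 30, closure and order are the same variable. Only τ + δ can be estimated, and no model separates the two. This holds under reading B as well: randomising the side does not randomise the order.

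**The case against.** The strongest reply has two parts. First, the ordinals are probably a slip. The envelope appears three times, the groups are named by closure alone in both sections, and the account of the adhesive operation under Surgical Technique and Application carries no ordinal. Secondly, the statements need not conflict. Reading B satisfies both Study Protocol sentences, with closure genuinely random with respect to side.

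Much of this stands. A reader might infer that the two rules cannot both describe the same 30 patients, that a 30:0 count would show no random draw took place, or that the trial should lose the word *randomized* altogether. The documents do not support any of these, because under reading B a 30:0 count is expected even though side was properly drawn. Nor is the Group 1 / Group 2 sentence the one that defines the groups; the definitions by closure come earlier in the same section.

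The reply does not dispose of the point. Reading B fits an envelope used at wound closure less well, and it leaves closure fully confounded with order. Only the envelope records can show that the ordinals are a slip.

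**Conclusion.** The allocation rule is stated in conflicting ways and must be reconciled. Loose wording is the likelier cause, but nothing in the text confirms it. What follows depends on what was done:

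- If closure order was drawn fairly, the fault is one of wording and the expected order bias is zero.
- If the draw concerned closure at each operation but suture was in fact always first, the conduct is inconsistent with a fair draw (probability 2^-30).
- If the draw concerned side and suture was always first, closure is randomised to side but carries the whole first-versus-second difference.

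A reader might infer that confounding has occurred. The documents do not show this: they give neither the order counts nor any order effect, so no size can be put on a bias. The 2^-30 figure assumes fair, independent draws under reading A and does not apply under reading B. The point concerns order only and says nothing about other sources of bias.

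**What to change.** 1. Reconcile the statements against the envelope records. State what the envelope assigned (closure at the first operation, or side) and when it was opened.
2. Report how many patients were suture-first and how many adhesive-first; the two counts should sum to 30. A mixed count rules out the literal fixed order but does not by itself prove randomisation, since alternation or operator choice can also produce one. The records are therefore needed as well as the counts.
3. If closure order was drawn, delete *first* and *second* from the Group 1 / Group 2 sentence and describe the groups by closure only, as the rest of the text already does.
4. If suture was always first, state that closure was not randomised with respect to operation order and that the closure comparison cannot be separated from order effects. Keep *randomized* only for what the records show was drawn, for example side.

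The cost is a check of the records, one tabulation, one sentence on the draw and one edited sentence. Only under item 4 does the trial's claim become weaker.

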## **Surgical Technique and Application**

The patients in the study were operated on by the same physician in the local operating room environment at the XXX University, Faculty of Dentistry, Department of Oral, Dental and Maxillofacial Surgery, in accordance with the rules of asepsis and antisepsis. It was planned to extract one mandibular wisdom tooth with mucosal or bone retention from each patient at a time. The tooth extraction on the other side was performed after the postoperative complications were eliminated and the extraction site wound healed and the mouth opening was restored. The wound closure technique to be used in the tooth extraction was determined by the closed envelope method and the surgical procedure was completed using a different technique in the other tooth extraction.

The oral cavity was cleaned with an antiseptic solution before surgery and the surgical field was prepared in accordance with aseptic conditions. Demographic data, preoperative mouth opening, facial landmark measurements, data regarding the impacted tooth and the operation were recorded in the anamnesis form. Inferior alveolar block anesthesia was performed with direct technique using 3 cc articaine hydrochloride 80 mg- Epinephrine 0.010 mg/ampule (Maxicaine VEM, Turkey) with 27 gauge dental syringes. The same equipment and local anesthetic were used for buccal anesthesia. Winter type envelope flap was preferred using a scalpel tip of No. 15 in the surgeries. Following the incision, the full thickness flap was lifted to reach the extraction area. In teeth with bone retention, the bone was lifted with a 1.6 mm diameter steel rond bur, fissure bur, surgical micromotor operating at 40,000 rpm and serum irrigation, and then the teeth were exposed. Then, the teeth were extracted with the help of a bein elevator. Irrigation was performed with physiological serum to prevent the heat generated during the bone removal procedure from damaging the living tissues. Teeth that could not be extracted in one piece due to their position were divided and extracted with a surgical micromotor. After extraction, the dental follicle was removed from the alveolar region with the help of curettes and clamps. The extraction socket and the bottom of the

mucoperiosteal flap were irrigated with plenty of physiological serum to remove bone particles and tissue residues.

The tension-free wound lips were closed by selecting the wound closure technique with the closed envelope method and providing appropriate procedures. The wound closure technique determined as suture wound closure was determined as the relevant dental control group. After the extraction socket was cleaned and bleeding control was provided, the wound lips were prepared without tension. The surgical site was closed primarily with 3/0, 16 mm 3/8 round needle atraumatic silk sutures. Postoperative recommendations were informed to the patient verbally and in writing. For infection control, 1000 mg amoxicillin+clavunate containing medication was prescribed 2x1 for 5 days. For pain control, 600 mg ibuprofen group analgesic was prescribed and recommended to be used 2x1. Cold compress was recommended for the first 8 hours after the operation for edema control. Appointments were made for the patient to come for the 3rd day and 1-week check-ups after the procedure. When the patient came for the check-up 1 week later, his sutures were removed.

The extraction of the tooth to which cyanoacrylate tissue adhesive would be applied was also performed with the same protocol and the surgical site was closed with cyanoacrylate tissue adhesive (Periacryl 90). While applying the tissue adhesive, the wound site was isolated from blood and saliva with an aspirator and sponge. Periacryl 90 liquid tissue adhesive was dropped onto a sterile perforated tray. Tissue adhesive was drawn into the applicator with a sterile applicator. The wound lips were brought together and the tissue adhesive was applied in a single layer with the applicator. Care was taken to ensure a tension-free closure. After the application, 30 seconds were waited for polymerization. The wound site was checked and the operation was terminated. Appointments were made for the 3rd day and 1-week check-ups after the procedure. It was recommended that the wound site not be traumatized with a toothbrush for 48 hours.

## **Statistical Analyses**

While evaluating the findings obtained in the study, NCSS (Number Cruncher Statistical System) 2020 Statistical Software (NCSS LLC, Kaysville, Utah, USA) program was used for statistical analyses. While evaluating the study data, quantitative variables were shown with mean, standard deviation, median, min and max values, and qualitative variables were shown with descriptive statistical methods such as frequency and percentage. Shapiro Wilks test and Box Plot graphics were used to evaluate the conformity of the data to normal distribution.

Student t-test was used in quantitative two-group evaluations showing normal distribution.

Mann Whitney-U test was used in the evaluations of variables not showing normal distribution according to two groups.

In intra-group comparisons according to follow-ups, Paired Samples test and Repeated Measures test were used in post hoc comparisons of variables showing normal distribution, and Bonferroni test was used.

Pearson Chi-Square test, Fisher's Exact test and Fisher Freeman Halton test were used in the comparison of qualitative data.

The results were evaluated at a 95% confidence interval and significance was at  $p < 0.05$ .

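### The between-closure test for each quantitative variable is picked from the data by an unspecified normality check, not stated to be on within-patient differences, and no over-time test is named for non-normal variables

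*Combined protocol and SAP*

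**What the plan says.** All of the relevant text is in Statistical Analyses.

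- **Check:** "Shapiro Wilks test and Box Plot graphics were used to evaluate the conformity of the data to normal distribution".
- **Two groups, judged normal:** "Student t-test was used in quantitative two-group evaluations showing normal distribution".
- **Two groups, judged non-normal:** "Mann Whitney-U test was used in the evaluations of variables not showing normal distribution according to two groups".
- **Change over follow-up:** "In intra-group comparisons according to follow-ups, Paired Samples test and Repeated Measures test were used in post hoc comparisons of variables showing normal distribution", with Bonferroni. No counterpart is named for variables that fail the check.
- **Level:** significance at p < 0.05. Sidedness is not stated.

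The design is within-patient. Study Protocol gives the size: "A total of 60 lower impacted wisdom teeth were extracted from 30 patients participating in the study". Surgical Technique and Application adds that, after the first extraction, "the surgical procedure was completed using a different technique in the other tooth extraction". Preoperative mouth opening and facial measurements are recorded, and check-ups follow on day 3 and at 1 week.

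**The concern.** Four things are left open.

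1. **Selection rule.** The observed data choose between a comparison of means and a comparison of ranks. One of the two criteria is a picture, and nothing says which prevails if they conflict.
2. **Unit of checking.** The check could be made per variable, closure or visit, or on pooled values. If it is made per visit, one outcome can get a t-test on day 3 and a rank test at 1 week, and the two results then answer different questions.
3. **What is checked.** With both closures in the same mouth, the distribution that matters for a paired comparison is that of the within-patient differences. The text does not say that these are examined. Switching to paired tests would not by itself settle this.
4. **A missing branch.** Change over visits has a named method only for variables judged normal.

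At stake are a consistent result for each outcome, a defined over-time analysis for skewed outcomes, and the power that the split-mouth design was meant to give.

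**Working it through.** The documents contain no sample-size or power figure, so there is none to reproduce.

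**Inputs from the documents:** 30 patients with one tooth per closure; post-operative visits on day 3 and at 1 week; level 0.05.

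**Assumptions, not in the documents:** Shapiro-Wilk at 0.05; check made per visit; Mann-Whitney used if either closure is flagged at that visit, otherwise Student t; two-sided tests; the distributions and correlations below.

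**Step 1. Chance flags when everything is normal.** With k independent checks, P(at least one flag) = 1 − 0.95^k.
- Two closures at one visit: 1 − 0.95² = 0.0975.
- Two closures at two visits: 1 − 0.95⁴ = 0.185.

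**Step 2. Chance that day 3 and 1 week get different tests.** If a visit is flagged with probability p, independently between visits, this is 2p(1 − p). The simulated column uses 4,000 runs with between-visit correlation 0.5 and independent closures.

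| Distribution | p (simulated) | 2p(1 − p) | Simulated switching |
|---|---|---|---|
| Normal | 0.102 | 0.184 | 0.18 |
| Lognormal, sigma 0.3 | 0.592 | 0.483 | 0.47 |
| Rounded 0-10 score | 0.612 | 0.475 | 0.45 |
| Lognormal, sigma 0.5 | 0.928 | 0.134 | 0.14 |
| Score piled up at zero | 1.00 | 0 | 0 |

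A separate simulation gave 17-19% for normal data and 35-42% for a gamma distribution with shape 4 (skewness 1). Switching is most frequent when the check is least decisive (p near 0.5) and disappears when skew is obvious.

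**Step 3. Type I error.** For equal variances and within-patient correlation ρ, the true variance of the mean difference is 2σ²(1 − ρ)/n. The unpaired test uses 2σ²/n, so its null rejection rate is about P(|Z| > 1.96/√(1 − ρ)).

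| ρ | 1.96/√(1 − ρ) | Approximation | Simulated, two-stage unpaired rule | Simulated, paired t |
|---|---|---|---|---|
| 0 | 1.960 | 0.050 | 0.049-0.052 | 0.044-0.051 |
| 0.3 | 2.343 | 0.019 | 0.021-0.023 | 0.048-0.053 |
| 0.5 | 2.772 | 0.006 | 0.006-0.007 | 0.042-0.048 |
| 0.7 | 3.578 | 0.0003 | 0.001-0.002 | 0.049 |

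Simulated ranges cover normal and lognormal (sigma 0.5) data. Signed-rank gave 0.046-0.054 throughout. The pretest adds nothing visible at ρ = 0. Ignoring the pairing pulls the rate well below 5% once ρ is positive.

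**Step 4. Power at ρ = 0.5 and a true difference of 0.5 SD (normal data).**
- Paired t: the SD of the differences is √(2(1 − 0.5)) = 1 SD, so the noncentrality is 0.5 × √30 = 2.74. On 29 df, power is about 0.75.
- Unpaired t: assumed SE √(2/30) = 0.258, true SE √(1/30) = 0.183, critical value 2.00 (58 df). Power is about P(Z > (2.00 × 0.258 − 0.5)/0.183), or 0.46 to 0.47.

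Simulation over the distributions tried gave 0.73-0.78 for the paired methods and 0.48-0.54 for the two-stage unpaired rule.

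**Step 5. The over-time branch.** This needs no arithmetic. The two-group sentences name a test for each verdict of the normality check; the follow-up sentence names tests for one verdict only.

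**The case against.** **Skewed outcomes are not dropped.** A reader might infer that a variable failing the check has no follow-up analysis at all. The text does not support this. Mann-Whitney U is not restricted to baseline, so the comparison of closures on day 3 and at 1 week has a stated method. What is unnamed is the within-group test over time, and an unnamed method is not a stated exclusion. This objection stands and limits the point.

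**Per-visit checking is not stated.** The text speaks of variables. It permits a check per visit but does not say that one was made, so the switching rates are conditional. The same mean, SD, median and range are reported for every quantitative variable, so the descriptive summaries do not switch. This also stands.

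**Error inflation.** A reader might infer that data-driven selection pushes type I error above 5%. That needs an analyst who takes the more favourable p-value, which nothing in the text suggests. For the stated unpaired tests it also needs sides that are close to uncorrelated. With positive correlation the stated route is conservative.

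**Symmetry of differences.** It is tempting to argue that differences are symmetric whenever the closures do not differ, so that a t-test is always safe. Between sides this needs exchangeability, not just equal means, and it says nothing about change from before to after surgery.

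**A mean difference is not the only defensible choice.** This is correct. Signed-rank could be the fixed primary test for some outcomes, and the fix allows for that.

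**Conclusion.** The point holds in limited form. The between-closure test is selected from the observed data without a complete rule, and nothing says that the within-patient differences are what is checked. No over-time test is named for non-normal variables.

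Under a per-visit check at an assumed 0.05, the test changes between day 3 and 1 week in roughly 17-19% of trials with normal data and 35-45% with moderate skew. The rate is about 14% with stronger skew and 0 for a score piled up at zero. These rates depend on assumed distributions and on a checking unit that the documents leave open.

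The cost is inconsistency, an undefined branch and lost power rather than false positives. Most of the measurable gain (power about 0.73-0.78 against 0.48-0.54 under the stated assumptions) comes from using one fixed paired method. The within-patient correlation is not given; at zero correlation that gain disappears.

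**What to change.** - Remove the normality-based choice of test. State one method per quantitative outcome, the same at every visit: the mean within-patient difference (adhesive minus suture) with a 95% CI, from a paired t-test or equivalent mixed model.
- Name the Wilcoxon signed-rank test as a fixed sensitivity analysis, reported whatever the main result. For outcomes known to be bounded or piled up at zero, it may be the fixed primary test instead.
- Use the same model for change over visits for all quantitative variables, so that no variable is left without a method.
- Use plots of differences or residuals for description only.
- The document is written in the past tense. If the analysis is already done, report which test was used for each outcome at each visit and add the fixed paired analysis, described as specified afterwards.

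**Cost:** wording, or some re-analysis of data already collected, and slightly less efficiency for the t-based method if the differences are heavy-tailed. No new data are needed.

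### Suture and adhesive are compared with independent-sample tests although each of the 30 patients receives both closures

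*Combined protocol and SAP*

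**What the plan says.** The Study Protocol section sets out the design: "A total of 60 lower impacted wisdom teeth were extracted from 30 patients participating in the study", and "The tooth extraction on the other side of the same patient was performed 3 weeks later". The groups are defined by side of the mouth, not by patient: "The side to which suture was applied after tooth extraction was determined as the control group". The Surgical Technique and Application section confirms that every patient receives both closures: once the envelope had fixed the closure for one tooth, "the surgical procedure was completed using a different technique in the other tooth extraction".

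For comparing two groups, the Statistical Analyses section names three sets of tests:

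- Normal data: "Student t-test was used in quantitative two-group evaluations showing normal distribution".
- Non-normal data: "Mann Whitney-U test was used in the evaluations of variables not showing normal distribution according to two groups".
- Categorical data: "Pearson Chi-Square test, Fisher's Exact test and Fisher Freeman Halton test were used in the comparison of qualitative data".

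Paired methods appear once, for another purpose: "In intra-group comparisons according to follow-ups, Paired Samples test and Repeated Measures test were used". No signed-rank test, McNemar-type test or model with a patient effect is named anywhere. Normality is assessed on the data in general, with no mention of within-patient differences.

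**The concern.** Two sites in one patient, treated by the same operator under the same protocol, are likely to give related results. Mouth opening and facial landmarks, which the protocol records, are measured on the same face both times. The tests listed for comparing groups treat the 60 teeth as 60 unrelated observations.

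If the two results from a patient are positively correlated, an unpaired test leaves the variation between patients in the standard error, although the design has removed it from the contrast. The p-values come out too large and the intervals too wide. With only 30 patients, the matching is the main source of precision, and the planned tests discard it. The practical risk is a non-significant result read as adhesive and suture performing alike, when the test was simply insensitive.

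**Working it through.** **Inputs from the documents.** 30 patients and 60 teeth, so 60 / 30 = 2 per patient, one under each closure. Significance is set at 0.05. The sidedness is not stated, and two-sided is assumed.

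**Assumed inputs.** The documents give no power calculation, effect size, SD or correlation, so there is no stated figure to reproduce. For illustration: equal SDs, a true difference of d = 0.5 SD, and a within-patient correlation ρ from −0.2 to 0.7.

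**Step 1, standard error.** For n pairs, the true variance of the mean difference is 2σ²(1 − ρ)/n. The unpaired test uses 2σ²/n. The planned standard error is therefore too large by a factor of 1/√(1 − ρ). At ρ = 0.5 this is 1/√0.5 = 1.41.

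**Step 2, interval width.** The unpaired interval uses the t quantile on 58 df (2.002) and the paired one uses 29 df (2.045). The width ratio is about (2.002/2.045)/√(1 − ρ) = 0.979/√(1 − ρ). At ρ = 0.5 this is 0.979 × 1.414 = 1.38.

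**Step 3, type I error.** A large-sample approximation is 2[1 − Φ(1.96/√(1 − ρ))]. It gives 1.9%, 0.56% and 0.03% at ρ = 0.3, 0.5 and 0.7. Simulation of 100,000 trials per scenario gives the slightly higher small-sample values in the table.

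**Step 4, power at d = 0.5.**

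- Paired t-test: noncentral t on 29 df with noncentrality 0.5√30/√(2(1 − ρ)). This is 2.31, 2.74 and 3.54 at ρ = 0.3, 0.5 and 0.7.
- Planned t-test: the expected statistic is about 0.5√(30/2) = 1.94, against a critical value of 2.00. Because the two nearly coincide, power stays just under 50% whatever ρ is.

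| ρ | SE ratio | Interval width ratio | Type I error, planned t | Power, planned t | Power, paired t |
|---|---|---|---|---|---|
| −0.2 | 0.91 | 0.89 | 7.4% | 48% | 40% |
| 0 | 1.00 | 0.98 | 4.9% | 48% | 47% |
| 0.2 | 1.12 | 1.09 | 2.9% | 48% | 55% |
| 0.3 | 1.20 | 1.17 | 2.0% | 47% | 61% |
| 0.5 | 1.41 | 1.38 | 0.7% | 47% | 75% |
| 0.7 | 1.83 | 1.79 | 0.08% | 47% | 93% |

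The paired t-test rejected in 4.9% to 5.0% of simulated null trials at every ρ.

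**Step 5, a binary outcome.** The assumed case is event rates of 20% and 50%, with a latent correlation of 0.6. In simulation, power is 62% for Fisher, 73% for Pearson chi-square, 78% for exact McNemar and 85% for mid-p McNemar.

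**The case against.** The strongest reply is that harm depends on a positive correlation, which the documents do not report. At ρ = 0 nothing is lost: the planned test has the right error rate and about one point more power. The two sides are also operated on some three weeks apart, so a value as high as 0.7 cannot be presumed. When the correlation is positive the error is conservative, so a significant result would stand and only null results are compromised. All of this is correct, and it limits the size of the loss. It does not justify the plan, whose validity would rest on an unexamined zero correlation; at ρ = −0.2 the same test is anti-conservative.

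A second reply is that the section never calls its t-test independent and never ties a test to an outcome, so a paired form might be meant. That reading is weak. A paired test is named separately for another purpose, the non-normal counterpart is Mann-Whitney U rather than signed-rank, and the categorical tests listed all assume independence.

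Two smaller points stand. The binary example is hypothetical, and with exact McNemar the gain over chi-square is only 78 − 73 = 5 points. Pairing also does not deal with session order. The Study Protocol section describes envelope randomisation but also links suture to the first tooth and adhesive to the second. If that order was followed, a paired test would estimate closure and session effects together. That is a separate issue.

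**Conclusion.** The concern holds. The stated tests for suture versus adhesive are wrong for a design in which every patient receives both; the section is not merely short on detail. Any positive correlation makes the nominal 5% test conservative. Over assumed correlations of 0.3 to 0.7, intervals are about 1.2 to 1.8 times too wide, and at a 0.5 SD difference the power forgone is 61 − 47 = 14 up to 93 − 47 = 46 percentage points. The mismatch follows from the text alone. Its direction rests on positive correlation, which is plausible here but not documented, and its size rests on the assumed correlation and effect. Because it affects the main treatment comparison and bears most on a finding of no difference, it must be corrected before results are interpreted.

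**What to change.** Rewrite the between-closure part of the Statistical Analyses section and re-run the comparisons:

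- **Quantitative outcomes:** paired t-test on the within-patient difference (adhesive minus suture) at each visit, or Wilcoxon signed-rank if the differences are clearly non-normal. Check normality on those differences. Report the mean difference with its paired 95% confidence interval.
- **Binary outcomes:** McNemar, stating in advance whether exact or mid-p.
- **Outcomes with more than two categories:** a paired test such as Stuart-Maxwell or Bowker.
- **Model-based alternative:** a mixed model with a random patient effect and fixed effects for closure, visit and session (first or second extraction). This uses the day-3 and 1-week visits together. It can separate closure from session only if the order of closures varied between patients.

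Report the observed within-patient correlation for each quantitative outcome, so that readers can see how much the pairing mattered. The cost is revised wording and a re-analysis of data already collected, provided each record can be linked to its patient. No new patients or measurements are needed.
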